3 SAFETY ENDPOINTS

Safety endpoints include:

- Treatment related Adverse Event (AE)
- Serious Adverse Event (SAE)
- All AE's

4 ANALYSIS SETS

The following analysis sets are defined for this study:

4.1 Full Analysis (FA) set

The Full Analysis (FA) set will include all the subjects randomized, including the subjects treated with the device up to May 31, 2019.

4.2 Intent-to-Treat (ITT) analysis set

The Intent to Treat (ITT) analysis set will include all randomized subjects who were treated with the device after May 31, 2019 (including self-practice). Per ITT principles, all subjects will be analyzed as randomized.

4.3 Modified Intent-to-Treat (mITT) analysis set

The mITT analysis set will include all subjects from the ITT analysis set who treat at least one eligible attack (excluding the "self-practice test"). Subjects in the mITT analysis set will be analyzed as treated.

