 - Subject will initiate the treatment procedure by turning on the device and the dedicated mobile application. The mobile application will guide the subject through the treatment procedure steps and will direct him/her to the study Patient Reported Outcome diary when required.
 - Prior to initiating the treatment, subject will report on the Patient Reported Outcome diary that:
 - He/she did not use analgesics or other pain relief drugs or cannabis within 4 hours period before the treatment.
 - Confirm no more than 30 minutes have passed since Migraine episode headache initiated.
 - Confirm that at least 48 pain free hours have passed since the subject previous Migraine episode.
 - Confirm he/she did not wake up with a Migraine headache.
- In case subject used analgesics or other pain relief drugs or cannabis within 4 hours period before the treatment initiation and/or more than 30 minutes passed from the start of the migraine episode and/or less than 48 pain free hours have passed since subject's previous Migraine episode and/or subject woke up with a Migraine headache, subject will be instructed to refrain from using the device and await his/her next migraine episode.
- Prior to initiation of treatment and no later than 30 minutes from Migraine headache pain initiation, subject will document on the Patient Reported Outcome diary his/her baseline migraine pain level (whereas 1=Mild pain, 2=Moderate pain, 3=Severe pain) and the most bothersome migraine-associated symptom (nausea, photophobia, phonophobia or none).
- Subject will then initiate the treatment along with the dedicated mobile application. The treatment will last 60±30 minutes. The Relivion™ device programmed treatment duration will be 1 hour. In case an earlier substantial pain relief is achieved, subject may stop treatment earlier but not less than 30 minutes from treatment start. If necessary, treatment can be paused by the

 Neurolief Brain Innovation	THE RIME STUDY: ABRIDGED CLINICAL INVESTIGATION PLAN	Doc No.: CL-CIP-001 Abridged Ref Rev: REV.2 / 11JUN2019 Pg. 27 of 41
--	---	--

subject and then be resumed. Treatment with total stimulation time of at least 30 minutes of a "pass" session on the device log timeline, will count as a completed treatment.

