- Subjects will be asked to refrain from consuming rescue medication/cannabis for at least 2 hours post treatment initiation. Subjects using rescue medication/cannabis prior to 2 hours post treatment initiation will be considered as failure (will be assigned the value of 0=no headache pain reduction) in the primary analysis.
- Subjects will document on the Patient Reported Outcome diary:
 - Pain according to a 4 points scale (0=no pain, 1=Mild pain, 2=Moderate pain, 3=Severe pain) at 1 and 2 hours \pm 30 minutes and at 24 hours \pm 6 hours post initiation of treatment.
 - Most Bothersome migraine-associated Symptom (MBS) other than a headache (chosen at baseline) improvement (yes/no) at 1 and 2 hours \pm 30 minutes post-treatment initiation.
 - Rescue medication intake.

8.1.7. Visit 4 - Termination visit (following 5 treated Migraine episodes or day 70 \pm 10, whichever comes first)

Written below are the assessments to be completed at Visit 4:

- After up to 5 migraine episodes within up to day 70 \pm 10, whichever comes first, subject will report to the clinic and return the device, Smartphone and hard copy subject diary, if applicable.
- Change in prophylactic anti-migraine & rescue headache medication will be documented.
- Subjects device Global Impression of Effect will be documented.
- Adverse events will be documented.
- Device logs, for each Migraine treated episode, will be downloaded by the study team (from study cloud database or from the device) to ascertain eligible treatments. An eligible treatment is defined as:
 - treatment meeting the basic criteria (*i.e.*, no analgesics or other pain relief drugs or cannabis within 4 hours period before the treatment initiation; no more than 30 minutes passed from the start of the migraine episode; more than 48 pain free hours have passed since subject's previous Migraine episode; and subject did not wake up with a Migraine headache); and
 - with total stimulation time of at least 30 minutes of a "pass" session on the device log timeline, where pass is defined as a minimal stimulation of 2mA delivered).

The characteristics of each treatment will be indicated on the subject CRF.

At this point subject's participation in this study will be over. The subjects will continue receiving medical care as per local standard of care, but not within the clinical study. Adverse Events that are still ongoing will be followed per local standard of care, but not within the clinical study.

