11.1. Study Endpoint Variables

11.1.1. Primary endpoint variable

The primary endpoint, the proportion of subjects reporting reduction of migraine headache pain 2 hours post treatment initiation from severe or moderate to mild or no pain, or from mild to no pain, in their first treated migraine attack, when using active combined occipital and supraorbital transcutaneous nerve stimulation compared to sham stimulation, in subjects suffering from acute migraine headache, will be measured in the form of a binary variable which will be assigned the value of "1" if the subject reports such headache pain reduction without having used rescue medications, and "0" otherwise. Rescue medication use within the 2 hours post treatment initiation will result in the subject will be coded as "0" automatically.

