On 02 July 2020 study enrollment was stopped, unfortunately, due to COVID-19; formal notice was sent out to the sites and ethical committees. Even though the company implemented all measures possible to ensure continued screening and randomization, subject retention and minimize loss to follow-up, but found that the completion of the originally planned randomized sample size was impossible .

Therefore, approximately 130 subjects for efficacy analysis were enrolled with 109 that have data for the primary endpoint, but that data remains blinded and has not yet been analyzed.

The approved study analysis plan utilizes a "sample size adaptive design" which calls for a single interim analysis for purposes of sample size adjustment, which was designed to occur when approximately 144 subjects had reached the primary endpoint. Due to the impact of the COVID-19 situation, the company would like to

modify the statistical plan while it remains blinded. The study has been stopped but the interim analysis has not been performed so that only one analysis - the final analysis - will be completed after data lock.

Based on the "Statistical Considerations for Clinical Trials During the COVID-19 Public Health Emergency" June 2020 FDA Guidance, and the fact that the Sponsor remains blinded to the treatment assignment and since no interim analysis was performed, no penalty to the alpha level is required. We shall address further analysis strategies in this revised SAP.

2 **EFFICACY ENDPOINTS**

2.1 **Primary Efficacy Endpoints**

The primary endpoint is the proportion (%) of patients reporting reduction in their pain level 2 hours post-treatment without rescue medications, from severe or moderate to mild or no pain, or from mild to no pain, in their first treated eligible migraine attack (excluding the "self-practice" treatment).

An eligible treatment is defined as a treatment meeting these basic criteria:

- no analgesics or other pain relief drugs or cannabis within 4 hours period before the treatment initiation; and
- no more than 30 minutes passed from the start of the migraine episode; and
- more than 48 pain free hours have passed since subject's previous Migraine episode; and
- subject did not wake up with a Migraine headache; and
- treatment with total stimulation time of at least 30 minutes of a "pass" session on the device log timeline, where pass is defined as a minimal stimulation of 2mA delivered).

2.2 **Secondary Efficacy Endpoints**

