5. Proportion of subjects who were free of pain in at least 50% of their eligible treated attacks at each timepoint.
6. Proportion (%) of attacks for which patients reporting reduction in their pain level without rescue medications from severe or moderate to mild or no pain, or from mild to no pain, from all treated eligible migraine attack at each timepoint (excluding the "self-practice" treatment).
7. Proportion of attacks for which subjects reporting improvement in their MBS other than a headache (if rescue therapy was not used), from all eligible treated migraine attack at each timepoint. MBS may be nausea, photophobia, phonophobia as defined by each subject prior to beginning of the treatment.
8. Proportion of attacks for which subjects reporting pain free (if rescue therapy was not used), from all eligible treated migraine attack at each timepoint.
9. Proportion of attacks for which subjects reporting freedom of MBS other than a headache (if rescue therapy was not used), from all eligible treated migraine attack at each timepoint. MBS may be nausea, photophobia, phonophobia as defined by each subject prior to beginning of the treatment.
10. Proportion (%) of patients with pain level moderate/severe at baseline reporting reduction in their pain level 1, 2 and 24 hours post-treatment without rescue medications, to mild or no pain, in their first treated eligible migraine attack (excluding the "self-practice" treatment).
11. Proportion (%) of patients with pain level moderate/severe at baseline reporting pain freedom at 1, 2 and 24 hours post-treatment without rescue medications, in their first treated eligible migraine attack (excluding the "self-practice" treatment).

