4.4 Per-protocol (PP) analysis set

The per-protocol (PP) analysis set will include all subjects in the mITT population who completed at least one eligible attack in compliance with the protocol and have no major protocol deviations. Subjects in the PP population will be analyzed as-treated.

Major protocol deviations defined as deviations which may impact subject safety, alter the risk/benefit ratio, compromise the integrity of the study primary end point data include, but are not limited to:

- Study treatment deviation for first eligible attack, e.g. baseline diary reported after treatment initiation, diary reported after treatment start, Baseline diary reported more than 30 minutes prior to the initiation of

treatment.

- PRO report outside of window for first eligible attack.

4.5

Statistical Analysis of Analysis Sets

As discussed in the introduction section to the SAP, a technical issue may have rendered the study device ineffective for those subjects treated prior to May 31, 2019. Since the treatments may not have been therapeutic, including them in the primary safety analysis may lead to under reporting of safety events. Consequently, the ITT data analysis set will serve as the principal data analysis set for the safety analyses. The safety analyses will also be performed on the Full Analysis set.

The mITT data analysis set will serve as the principal data analysis set for the efficacy analyses.

The primary and secondary efficacy assessments will also be performed on the per protocol (PP) and the ITT analysis sets.

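### The scored attack must reach 30 minutes of pass-level stimulation, so a shorter, rescued attack goes unscored and a later one can replace it; no analysis shown tests the effect

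*SAP*

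**What the plan says.** **Which attack is scored.** SAP 2.1 uses the first treated eligible attack and lists five criteria. Four are fixed before the device is switched on: no analgesic or cannabis in the previous 4 hours, onset no more than 30 minutes ago, 48 pain-free hours, and not woken by migraine. The fifth is "treatment with total stimulation time of at least 30 minutes of a" session logged as a pass (2 mA minimum). Protocol 8.1.7 defines an eligible treatment in the same way. Subjects may treat up to 5 attacks (Protocol 8.1.6).

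**Which subjects.** SAP 4.3: "The mITT analysis set will include all subjects from the ITT analysis set who treat at least one eligible attack", analysed as treated. SAP 4.5: "The mITT data analysis set will serve as the principal data analysis set for the efficacy analyses", and "The primary and secondary efficacy assessments will also be performed on the per protocol (PP) and the ITT analysis sets".

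**Rescue.** Protocol 8.1.6: "Subjects using rescue medication/cannabis prior to 2 hours post treatment initiation will be considered as failure". Protocol 11.1.1: "Rescue medication use within the 2 hours post treatment initiation will result in the subject will be coded as" zero. Protocol 8.5 differs: diary data after rescue are left out of the analysis of the time point concerned.

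**Wording on the attack.** The statistical part of the Protocol synopsis and Protocol 11.1.1 refer to the first treated attack without requiring eligibility. The synopsis endpoint entry, Protocol 4.2.1 and 11.7.5, and SAP 2.1 require it. The SAP Introduction says the SAP prevails over the Protocol.

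**The concern.** Four of the criteria cannot be affected by the treatment of that attack. The fifth can: a session may end short because of discomfort, lack of effect, relief or a device fault. Selecting the scored attack on it means that the comparison is no longer made on a unit fixed before treatment, and randomisation does not protect it. The active and sham settings differ in pulse frequency (80 Hz against 0.33 Hz), phase duration and maximum intensity (Protocol 5.3). Different rates of short sessions are therefore plausible, though not shown.

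Two cases follow.

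- **Replacement.** A subject has a short, rescued attack and later treats an eligible one. The later attack supplies the outcome.
- **Exclusion.** A subject never has an eligible attack and leaves the mITT set.

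At stake is whether a reader of the pivotal result can tell if it depends on attacks that were passed over.

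**Working it through.** **1. Does any analysis shown restore a replaced attack?**

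| Analysis | Reaches replacement? |
|---|---|
| Multiple imputation, observed data, best and worst case (Protocol 11.7.5) | No. They act on missing data or early withdrawal, and this subject has a 2-hour score from the later attack. |
| Dropout/AE rule (Protocol 11.7.5) | No, unless the subject withdrew for an adverse event or intolerance, or has no post-baseline pain score. |
| Per-protocol set (SAP 4.4) | No. It is a subset of mITT. |
| ITT set (SAP 4.2, 4.5) | No. It changes the subjects, not the attack scored. |
| Multi-attack analyses (SAP 2.3) | No. They count eligible attacks only: "from all treated eligible migraine attack at each timepoint". |

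Exclusion is partly covered by the ITT run with imputation. The text does not settle whether such a subject falls under the Dropout/AE rule or under the zero-otherwise coding of Protocol 11.1.1.

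**2. The plan's own figure.** For 45% against 25%, two-sided 5% and 80% power, the pooled-variance formula gives

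n = [1.96√(2×0.35×0.65) + 0.8416√(0.45×0.55 + 0.25×0.75)]² / 0.20² = 88.1, so 89 per group.

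The plan states 90, which gives 80.8% power. The sample size reproduces and is not in question.

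**3. Illustration of size.** The documents give no count of skipped attacks, so the rates below are assumed. The SAP Introduction reports 109 subjects with primary data; a 55/54 split is assumed from 1:1 allocation. True response is set at p = 0.30 in both arms.

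Let f be the share of an arm whose failed first attack is skipped, and ρ the within-subject correlation. After a failure the next attack responds with probability p(1−ρ), so the scored rate is p + f·p(1−ρ). The chance of a significant result favouring active is

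Φ[(a − b − 1.96·SE₀)/SE₁],

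where a and b are the scored active and sham rates, SE₀ is the pooled and SE₁ the unpooled standard error.

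With f = 10% active, 0% sham and ρ = 0: a = 0.30 + 0.10×0.30 = 0.330, b = 0.300, SE₀ = 0.0890, SE₁ = 0.0889. Then (0.030 − 0.1744)/0.0889 = −1.62, giving 5.2% (exact binomial 5.3%).

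| Skipped failures, active / sham | ρ | Scored rates | False favourable |
|---|---|---|---|
| 10% / 0% | 0 | 0.330 / 0.300 | 5.2% |
| 10% / 0% | 0.3 | 0.321 / 0.300 | 4.2% |
| 10% / 0% | 0.5 | 0.315 / 0.300 | 3.7% |
| 5% / 0% | 0 | 0.315 / 0.300 | 3.7% |
| 10% / 5% | 0 | 0.330 / 0.315 | 3.6% |
| 10% / 10% | 0 | 0.330 / 0.330 | 2.5% |
| 0% / 10% | 0 | 0.300 / 0.330 | 1.1% |

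If skipped attacks were successes (10% of active, ρ = 0), the active rate is 0.30 − 0.10×0.70 = 0.230 and the chance falls to 0.3%.

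**4. Sensitivity of one result.** Near the planned rates, 25/55 against 14/54 gives p = 0.033 (chi-squared, no continuity correction). If one active responder had replaced a rescued first attack, 24/55 gives p = 0.052. One in each arm (24/55 against 13/54) gives p = 0.031.

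**The case against.** A reader might infer that the plan breaks its own rescue rule. The documents do not support that. In the synopsis endpoint entry, Protocol 4.2.1 and 11.7.5, and SAP 2.1 the endpoint is read in the first eligible attack, so the rule is limited to that attack. An attack that reaches 30 minutes of pass stimulation and is then rescued is still a failure. What remains is a conflict with the passages that omit eligibility, and with Protocol 8.5.

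A reader might also infer that the SAP counts stimulation time differently from the Protocol. It does not. Protocol 8.1.6 says "subject may stop treatment earlier but not less than 30 minutes from treatment start" and allows pauses, but then counts total stimulation time, as the SAP does. The tension lies within 8.1.6: a paused session can respect the instruction and still fall short.

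A bias in favour of active is not shown either. The 10% against 0% case means that one in seven active failures (0.10/0.70) was stopped short and rescued, and none in sham. Nor can the roughly 21 of 130 subjects without primary data be attributed to this criterion.

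Frequency is limited by the 2 mA check at Visit 2 (Protocol 8.1.3), the pass-level practice session and log-based retraining (8.1.5, 8.1.6), and the 30-minute instruction. The criterion is read from device logs in a blinded trial. A minimum-exposure condition can be a legitimate primary choice. The SAP shown is abridged, and the full version may contain further analyses. All this stands and lowers the weight of the point, but none of it scores a replaced attack.

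**Conclusion.** The structural point holds on the text shown. One eligibility criterion is decided after treatment starts, it determines which attack is scored and who enters the principal efficacy set, and no analysis shown restores a replaced attack.

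Size and direction of any bias are unknown. Short sessions ended for discomfort or lack of effect would remove failures; those ended for relief would remove successes. Under the assumed rates, skipping failures only in active raises the false-favourable chance from 2.5% to between 3.7% and 5.2%, depending on within-subject correlation. Equal skipping has no effect under the null, and the reverse lowers the chance. These figures rest on 30% response, a 55/54 split and assumed skipping rates; they show sensitivity and are not estimates for this trial.

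The point should be fixed because the remedy is cheap and nothing specified would reveal the problem. It is no reason to discard the mITT analysis. Confidence is medium, because the frequency is unknown and the SAP is abridged.

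**What to change.** Keep the mITT primary analysis and specify the following before unblinding.

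1. **One sensitivity analysis, as randomised, on the SAP ITT set.** Score the first attack after 31 May 2019 in which the device was started and the four pre-treatment criteria held, whatever the stimulation time. Rescue before 2 hours is a failure. Handle missing 2-hour scores and subjects with no such attack by the imputation rules already in Protocol 11.7.5. Score them as non-responders only in a separate run, so that the effect of replacement can be seen apart from missing data.
2. **One table.** By arm and reason, including device failure: every started attack skipped as ineligible, and every subject without an eligible attack.
3. **SAP 4.3.** Group the mITT efficacy analysis as randomised. This changes results only if a wrong device was used.
4. **Wording.** Reconcile the passages that say first treated with those that say first treated eligible, and Protocol 8.5 with the rescue-as-failure rule.

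The cost is SAP text, one analysis with a supplementary run, and one table. Device logs, treatment characteristics and 2-hour diaries are already collected (Protocol 8.1.6, 8.1.7).

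The downside is dilution of the sensitivity estimate. In the non-responder run, suppose all of the roughly 21 (130 − 109) without data count as failures, split evenly. Then 45% becomes 0.45×54.5/65 = 37.7% and 25% becomes 0.25×54.5/65 = 21.0%, a difference of 16.8 points (before rounding) instead of 20.

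### Subjects randomised on or before 31 May 2019 enter the SAP's efficacy sets only through later device use, and mITT and PP are grouped as treated: a cheap fix before data lock

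*SAP*

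**What the plan says.** **Principal efficacy set.** SAP 4.5: "The mITT data analysis set will serve as the principal data analysis set for the efficacy analyses". SAP 4.3 defines it: "The mITT analysis set will include all subjects from the ITT analysis set who treat at least one eligible attack". Under SAP 2.1 an eligible attack needs, among other conditions, at least 30 minutes of logged stimulation at 2 mA or more. SAP 4.3 adds: "Subjects in the mITT analysis set will be analyzed as treated". For PP, a subset of mITT, SAP 4.4 says: "Subjects in the PP population will be analyzed as-treated". Protocol 11.6 already had mITT as the efficacy set and the same as-treated grouping.

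**Supporting efficacy sets.** SAP 4.5: "The primary and secondary efficacy assessments will also be performed on the per protocol (PP) and the ITT analysis sets". Protocol 11.6 defined ITT as all randomised subjects. In SAP 4.2 the set "will include all randomized subjects who were treated with the device after May 31, 2019 (including self-practice"), analysed as randomised. The SAP Introduction says that the SAP prevails over the protocol.

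**Full Analysis set.** SAP 4.1 puts every randomised subject in it. SAP 4.5 names it for safety only: "The safety analyses will also be performed on the Full Analysis set". The main safety set is ITT: "Consequently, the ITT data analysis set will serve as the principal data analysis set for the safety analyses".

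**Reason for the cut.** The SAP Introduction reports a device fault in the initial phase that may have made treatments ineffective. It says ethics committees approved up to 50 additional subjects, that the data are still blinded, and that no analysis had been done.

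**The concern.** A comparison of randomised arms is protected when membership of the analysis set is settled at randomisation. Membership of mITT is settled later, by use of the assigned device. The arms receive different stimulation (Protocol 5.3). Subjects who do not reach 2 mA at Visit 2, or who have no eligible self-practice session, are withdrawn (Protocol 8.1.3 and 8.1.5). Exclusion could therefore differ by arm. That is an inference from the design; no imbalance is reported.

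The usual check on such a set is an as-randomised run on everyone randomised. The SAP's ITT run serves that purpose well for subjects randomised after the cut. It serves less well for those randomised on or before the cut, called straddling subjects here if they used the device again afterwards. A straddling subject is counted; a subject randomised on the same day who stopped using the device by 31 May is not. If continuing is related to arm and to response, the supporting run carries the same selection that it is meant to test.

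**Working it through.** **1. The plan's own figure.** Protocol 11.3 assumes 45% v 25%, two-sided 5%, 80% power. With the pooled-variance formula, n per arm = [1.960·√(2·0.35·0.65) + 0.842·√(0.45·0.55 + 0.25·0.75)]² / 0.20² = 88.1, so 89 per arm (178). The plan's 90 per arm (180) gives 80.8% power, and 180/0.90 = 200 enrolled. The planning rates reproduce and are used below.

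**2. The sets side by side.**

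| Set | Membership | Grouping | Efficacy run in SAP |
|---|---|---|---|
| Protocol ITT | all randomised | as randomised | replaced by the SAP |
| SAP ITT | any device use after 31 May 2019 | as randomised | supporting |
| SAP mITT | SAP ITT with an eligible attack | as treated | principal |
| SAP PP | mITT, compliant | as treated | supporting |
| SAP Full Analysis | all randomised | not stated | none named |

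Protocol 8.1.3 lists self-practice at Visit 2, after randomisation in the same visit. SAP 4.2 counts self-practice. So for subjects randomised after the cut, SAP ITT is close to all randomised.

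**3. Who could straddle.** The first day after the cut is 1 June 2019.
- Protocol 8.1.5 and 8.1.6 count the treatment period, up to Day 80, from Visit 2. 1 June minus 80 days gives a randomisation on 13 March 2019 at the earliest.
- Protocol 7.2 counts the 80 days from Visit 1. Visit 1 is then 13 March, and Visit 2, 28 to 38 days later, is 10 to 20 April.

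The two anchors conflict and must be reconciled. Neither document says how many straddling subjects exist.

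**4. Subjects without primary data.** The SAP Introduction gives about 130 subjects for efficacy and 109 with primary data: 130 − 109 = 21, and 21/130 = 16%. How many of the 21 lie outside mITT, and in which arm, is not given. Some may be inside mITT with a missing 2-hour report.

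**5. Illustration of exclusions.** Assume 65 per arm, 25% response in both arms, and all 21 excluded. False success is the exact sum of binomial probabilities over outcomes with z > 1.96 favouring active, where z = (a/n_A − s/n_S) / √[p̄(1−p̄)(1/n_A + 1/n_S)]. Nominal is 2.5%; the full 65 v 65 gives 2.6%.

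| Excluded, active/sham | mITT, excluded all non-responders | mITT, excluded respond at 25% | Non-response scoring of all 130, excluded respond at 25% |
|---|---|---|---|
| 11/10 | 3.3% | 2.5% | 1.9% |
| 13/8 | 6.2% | 2.7% | 1.1% |
| 17/4 | 13.5% | 2.6% | 0.3% |
| 10/11 | 2.6% | 2.5% | 2.5% |
| 8/13 | 1.4% | 2.5% | 4.1% |
| 4/17 | 0.4% | 2.4% | 9.6% |

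Fisher's test gives 2.9%, 4.7% and 11.9% in the first three rows of the first result column. If the excluded are all non-responders, non-response scoring on all 130 stays at 2.6% by construction. Each approach is distorted under one assumption and sound under the other.

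**6. Illustration of straddling subjects.** Assume mITT of 54 v 55, half the straddling subjects active, and everyone else at 25%. If the active ones respond at 40% or 50%, 10 straddling subjects (5 active) give 3.7% or 4.6%, and 20 (10 active) give 5.2% or 7.7%. If they respond at 25%, it stays 2.5%.

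**7. Power at 45% v 25%.** mITT of 54 v 55: 60%. Without 10 straddling subjects (49 v 50): 56%. Without 20 (44 v 45): 52%.

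**The case against.** The case against giving this weight is strong, and most of it stands.

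- A reader might infer that the SAP leaves no sound as-randomised check, and so that the efficacy result is biased. The documents do not support that. SAP ITT is analysed as randomised, is nearly complete after the cut, and has its own efficacy run. Protocol 11.7.5 adds multiple imputation, non-responder scoring, and best- and worst-case runs.
- A reader might also infer that ITT was narrowed to favour the device. The SAP gives a technical reason and reports the data as blinded and unanalysed.
- mITT was the efficacy set in the protocol and matches an endpoint defined on the first eligible treated attack.
- The sizes above rest on assumed splits and response rates. If exclusion were unrelated to arm, 17 or more of the 21 would be active with probability of only about 0.2% (21 drawn from 65 + 65).
- As-treated grouping matters only if devices were crossed, and no crossing is reported.
- Both documents are abridged, so a full SAP may already deal with this.

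What this does not remove is the membership rule for subjects randomised on or before the cut. Imputation fills in outcomes for subjects who are in a set; it cannot restore those whom the set leaves out. An efficacy run on the Full Analysis set is not the answer either, because it would bring back treatments that the SAP regards as possibly ineffective.

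**Conclusion.** The point holds at modest weight: it should be fixed, mainly because the fix is cheap. The definitions show that straddling subjects enter ITT, and possibly mITT, through device use after randomisation, and that mITT and PP are grouped as treated. The size is unknown. If there are no straddling subjects and no crossed devices, the gap has almost no effect. If 10 to 20 exist and re-use was selective as in step 6, false success is 3.7% to 7.7% against 2.5%. For mITT exclusions in general, a near-even 11/10 split gives 3.3%, and splits with more sham exclusions lower the rate. All of these are illustrations, not estimates of bias in this trial. Confidence is medium, given the abridged documents.

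**What to change.** Before data lock, in SAP 4.2 to 4.5:

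- **(a)** Analyse mITT and PP as randomised. Results change only if devices were crossed.
- **(b)** Keep SAP 4.2 for safety and as the base for mITT. Add a separately named supporting efficacy set: all subjects randomised after 31 May 2019, treated or not, as randomised. Run the primary endpoint on it twice, once with the protocol's multiple imputation and once with no eligible attack or no 2-hour report scored as non-response. Protocol 11.1.1 and 11.7.5 already contain the basis for both. Read the two runs together, since neither is unbiased alone.
- **(c)** Show the mITT result with and without subjects randomised on or before the cut, as a sensitivity check, and state how many there are in each arm.
- **(d)** Tabulate exclusions from each set by arm with reasons, extending the list promised in Protocol 11.7.4.

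**Cost.** Wording, one added set and a few tables; no new data or patients. The principal mITT analysis keeps its members and, to all intents, its power, and the safety set is unchanged. Supporting estimates may look less favourable. If 45% v 25% holds within mITT, power for mITT v the non-response run is 60% v 54% (exclusions 11/10), 61% v 43% (13/8) or 60% v 70% (8/13). The run without straddling subjects has the lower power shown in step 7.
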